# The safety endpoints are:

- Incidence of Adverse Events (AEs);
- Change in vital signs;
- Change in 12-lead Electrocardiogram (ECG) parameters;
- Incidence of clinically or hemodynamically significant episodes of supraventricular or ventricular arrhythmias detected by continuous ECG dynamic monitoring;
- Change in laboratory parameters (hematology, blood chemistry and urinalysis);
- Change in renal function (Estimated glomerular filtration rate (eGFR));
- Change in cTnT;
- Incidence of cTnT elevation relative (>50% or >20% relative increase over the cTnT levels at baseline, for patients with cTnT basal levels at baseline < or ≥ of the 99% Upper Reference Limit (URL, as defined for the Roche hs test to be 14 ng/L) respectively;
- Mortality at Day 30.

# The PK parameters are the following:

- Istaroxime plasma concentrations: Cmax, Tmax, AUC0-t, AUC0-∞, λz, t½, ClT, MRT, Vss, Vz;
- Istaroxime urine concentrations: Ae, Ae%, ClR;
- PST2915, PST2922, and PST3093:  $C_{max}$ ,  $T_{max}$ ,  $AUC_{0-t}$ ,  $AUC_{0-\infty}$ ,  $\lambda_z$ ,  $t_{\frac{1}{2}}$  and, if possible,  $A_e$  and  $A_e$ %.

# 4.0 STUDY DESIGN

This is a phase II, multicenter, randomized, double-blind, placebo-controlled, parallel group study.

96 Chinese patients and 24 Italian patients will be randomly assigned to one of two doses of istaroxime or placebo in a 2:1 ratio within two sequential cohorts of 60 patients each.

1.0/30/10/2018 Page 9 of 28

This 31-day study includes a screening period (Day -1), a treatment period (Day 1), a post-treatment period (Days 2-4), and a follow-up period (which includes one patient visit on Day 30).

When a patient is considered fully eligible (i.e. s/he fulfills all the inclusion criteria and does not meet any exclusion criteria as stipulated), the patient will be randomized.

Treatment details are presented below:

**Cohort I**: 0.5 µg/kg/min istaroxime or placebo (40 patients randomized to istaroxime 0.5 µg/kg/min group and 20 patients randomized to placebo group).

Istaroxime 0.5  $\mu$ g/kg/min (30  $\mu$ g/kg/h) continuous i.v. infusion for 24 hours not exceeding 72 mg per 24 hours for patients with body weight > 100 kg.

**Cohort II**: 1.0 μg/kg/min istaroxime or placebo (40 patients randomized to istaroxime 1.0 μg/kg/min group and 20 patients randomized to placebo group).

Istaroxime 1.0  $\mu$ g/kg/min (60  $\mu$ g/kg/h) continuous i.v. infusion for 24 hours not exceeding 144 mg per 24 hours for patients with body weight > 100 kg.

A total of 96 Chinese and 24 Italian patients hospitalized with ADHF not requiring inotropic therapy at inclusion into the study (according to the opinion of the Investigator) and not presenting signs and/or symptoms of severe low output state or peripheral hypo perfusion will be randomized.

# 4.1 SAMPLE SIZE

No formal sample size calculation has been calculated since there is no preliminary study to evaluate these endpoints at 24 hours after the infusion start.

In a previous study (Gheorghiade M. et al. Haemodynamic, echocardiographic, and neurohormonal effects of Istaroxime, a novel intravenous inotropic and lusitropic agent: a randomized controlled trial in patients hospitalized with heart failure. J Am Coll Cardiol. 2008; 51(23): 2276-85), there was a statistically significant decrease of the primary efficacy endpoint with istaroxime 0.5 µg/kg/min respect to placebo at 6 hours (twenty-nine patients in both groups). Since this study will investigate the primary efficacy endpoint at 24 hours and it is supposed that the profile at 24 hours should be similar to the one at 6 hours, it is expected that forty patients per group will be sufficient to evaluate a potential difference between istaroxime groups and placebo group on the primary efficacy endpoint at 24 hours.

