The primary comparison will be $0.5 \mu g/kg/min$ dose of istaroxime versus placebo at 24 hours. Highest dose of istaroxime (1.0 $\mu g/kg/min$) versus placebo will be tested as a secondary comparison.

Additional analyses separated by cohort will be implemented for sensitivity purpose.

Secondary efficacy endpoints

The following secondary endpoints:

- Change from baseline to 24 hours in the treatment period Day 1 (addressing the differences between the changes at 6 and 24 hours from baseline) of the following Echo-Doppler parameters:
 - o LV Ejection fraction (EF)
 - o LV end systolic and end diastolic volumes
 - o Stroke volume index (SVI)
 - o E, A and E/A ratio
- Change from baseline to 24 hours in the E/Ea ratio assessed by tissue Doppler (difference between the changes at 6 and 24 hours from baseline)
- Others Tissue Doppler parameters such as Sa, Da and Aa
- Changes in dyspnoea using VAS score will be analysed using a mixed model for repeated measures similar to the one used for the primary efficacy endpoint.

A global test considering multiple echocardiographic parameters at 6 and 24 hours will also be performed.

AUC on changes in dyspnea by VAS and changes in BNP will be analyzed using an ANCOVA model with treatment, centre, gender, baseline cTnT (normal <URL, abnormal ≥URL) and atrial fibrillation (Yes/No) as fixed effects and baseline dyspnea as covariate.

Number and proportion of patients with:

- hospital readmissions or emergency visits for cardiovascular reasons within Day 30
- episodes of worsening HF defined by the need to increase the dose or reinitiate i.v. therapy with diuretics and/ or other inotropic agents during the hospitalization

will be summarized by treatment groups using descriptive statistics.

Length of hospitalization will be summarized by treatment group using descriptive statistics.

Safety endpoints

The number and the percentage of patients experiencing adverse events, adverse drug reactions, serious adverse events and adverse events leading to study withdrawal will be summarized by treatment group. Adverse events will also be summarized by treatment group by means of System Organ Class and Preferred Term using the MedDRA dictionary.

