# 1.1 CHANGES FROM PROTOCOL

The analysis of echocardiographic parameters is changed from the protocol:

- The analysis of echocardiographic parameters will be performed separately for each cohort, instead of performed on the combined cohorts.
- An analysis of variance (ANOVA) model with treatment as covariate is now the primary analysis, instead of a mixed model for repeated measures (MMRM) including treatment and additional covariates.
- Missing response data will not be imputed in the ANOVA analysis.

The justification for these changes are documented in the Memo to File prepared by [name], dated 24Oct2018, entitled: Change in analysis of echocardiographic parameters.

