# 7.0 STATISTICAL METHODOLOGY

## 7.1 HANDLING OF MISSING DATA

The number of patients with missing data will be presented under the "Missing" category, if present. Missing values will be included in the denominator count when computing percentages.

When continuous data are being summarised, only the non-missing values will be evaluated for computing summary statistics.

Missing or incomplete data will be treated as described in sections 6.1, 6.3 and 6.4.

There will be no imputation of missing echocardiographic data.

Other critical missing data will be discussed prior to treatment unblinding, if any. Decisions will be taken during the blind review of the data and will be fully documented in the Data Review Report.

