# 7.4 GENERAL METHODOLOGY

Descriptive statistics will be provided for all variables in the summary tables by treatment group according to the type of variable summarized.

Quantitative variables will be summarised by using n, mean, standard deviation (SD), 95% confidence interval (CI) of the mean, median and range (minimum and maximum). Categorical variables will be summarised by using frequency distributions and percentages.

Hypothesis testing will be carried out at the alpha = 0.05 level (two-sided) when comparing treatments. For all inferential analyses, p-value will be rounded to three decimal places. Statistical significance will be declared if the rounded p-value will be less than or equal to 0.05.

Statistical analyses will be carried-out pooling together the patients treated with placebo in the two groups with the exception of the echocardiographic parameters that will be analysed separately for each cohort.

All data collected in the CRF will be presented in the listings.

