#### 7.7 ANALYSIS OF EFFICACY

# 7.7.1 Primary efficacy endpoint

Analysis will be performed separately for each cohort on ITT and PP populations.

E/Ea ratio will be summarized at each timepoint by treatment group by means of descriptive statistics.

Comparisons between treatment groups will be done using an ANOVA with change from baseline in E/Ea at 24 hours as dependent variable, and treatment as covariate.

The number of patients and the number of patients considered in the model will be provided by treatment. P-values of the fixed effects and covariates will also be presented.

The adjusted means for treatments and 95% CIs will be presented. The difference between the adjusted means for Istaroxime groups versus Placebo will be calculated with the 95% CIs and p-values.

The primary comparison will be Istaroxime 0.5  $\mu$ g/kg/min versus Placebo at 24 hours based on Cohort 1 subjects only. Highest dose of Istaroxime (1.0  $\mu$ g/kg/min) versus Placebo will be tested as a secondary comparison based on Cohort 2 subjects only.

The same analysis will be repeated for change from baseline in E/Ea at 6 hours. All treatment comparisons at 6 hours will be secondary analyses.

E/Ea ratio will also be summarized separated by cohort at each timepoint by treatment group by means of descriptive statistics.

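### SAP 4.1 still relies on forty patients per group, but the cohort-by-cohort primary comparison is 40 istaroxime versus 20 placebo, equivalent to 26.7 per group

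*SAP*

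**What the plan says.** SAP 4.1 repeats the sample size text of Protocol 14.2. It states that no formal calculation was made. It then cites an earlier study with 29 patients in each group, in which E/Ea fell significantly at 6 hours on 0.5 µg/kg/min relative to placebo. It supposes that the 24-hour profile will resemble the 6-hour one and concludes that "forty patients per group will be sufficient to evaluate a potential difference between istaroxime groups and placebo group".

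SAP 4.0 describes two sequential cohorts of 60, randomized 2:1. Each has 40 patients on istaroxime, and for placebo the text reads "group and 20 patients randomized to placebo group".

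Under the protocol the main E/Ea model covered both cohorts, and the by-cohort analysis was supportive: "Additional analyses separated by cohort will be implemented for sensitivity purpose" (Protocol 14.2). The final SAP reverses this:

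- SAP 1.1: "The analysis of echocardiographic parameters will be performed separately for each cohort, instead of performed on the combined cohorts".
- SAP 7.4: analyses are done "pooling together the patients treated with placebo in the two groups with the exception of the echocardiographic parameters".
- SAP 7.7.1: the primary comparison is 0.5 µg/kg/min "versus Placebo at 24 hours based on Cohort 1 subjects only". The 1.0 µg/kg/min comparison likewise uses Cohort 2 only.
- SAP 7.1: "There will be no imputation of missing echocardiographic data".

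**The concern.** The forty-per-group statement was coherent under the protocol, where 20 + 20 placebo patients made a group of forty. It went out of date when the echocardiographic analysis was split by cohort. SAP 1.1 lists three changes and none concerns sample size; the version history mentions only the change of model.

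Two things follow. A reader of 4.1 would believe that the primary comparison has twice as many placebo patients as it has. And the reasoning in 4.1, that forty per group should be enough where 29 per group had been, no longer applies, because 40 versus 20 is effectively smaller than 29 versus 29.

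The documents give no SD, target effect or power for E/Ea, so 4.1 is the only guide to planned precision. That matters most if the primary result is not significant and someone has to judge what the trial could have detected.

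**Working it through.** **Inputs.** Stated size: 40 per group (SAP 4.1). Earlier study: 29 versus 29 (SAP 4.1). Randomized per cohort: 40 istaroxime, 20 placebo (SAP 4.0). Two-sided alpha 0.05 (SAP 7.4). No SD for E/Ea change is given, so results are in SD units, assuming a common SD and complete 24-hour data.

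**Reproducing the stated figure.** There is no power calculation to reproduce. As a head count, forty placebo patients arise only as 20 + 20 across cohorts, giving 40 + 40 + 40 = 120. Within one cohort the comparison is 40 versus 20.

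**Equal-group equivalent.** 2 / (1/40 + 1/20) = 2 / 0.075 = 26.67 per group.

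**Standard error and precision.** SE = √(1/n₁ + 1/n₂). Half-width = t(0.975, n₁ + n₂ − 2) × SE. The detectable difference uses the noncentral t at 80% power.

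| | 40 vs 20 | 40 vs 40 | 29 vs 29 |
|---|---|---|---|
| SE (SD units) | 0.2739 | 0.2236 | 0.2626 |
| 95% CI half-width (SD units) | 0.548 | 0.445 | 0.526 |
| 80%-power difference (SD units) | 0.780 | 0.634 | 0.749 |

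- Against 40 versus 40: information 0.050 / 0.075 = 0.667; SE ratio 0.2739 / 0.2236 = 1.225.
- Against 29 versus 29: information (2/29) / 0.075 = 0.920; SE ratio 0.2739 / 0.2626 = 1.043.

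**In E/Ea units (illustration only).** Protocol 1.2 reports E/Ea changes of −3.8 (p = 0.03) at 0.5 µg/kg/min and −1.12 (p = 0.059) at 1.0 µg/kg/min, and does not say clearly that these are differences from placebo. Read as t-tests with 29 per group, they imply SDs of about 6.5 and 2.2. These disagree too much for either to serve as the planning SD, so a range is shown. The power columns suppose a true difference of 3.8.

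| Assumed SD | 80%-power difference, 40 vs 20 | Power, 40 vs 20 | Power, 40 vs 40 |
|---|---|---|---|
| 2.2 | 1.7 | >99% | >99% |
| 4 | 3.1 | 93% | 99% |
| 5 | 3.9 | 78% | 92% |
| 6.5 | 5.1 | 56% | 73% |
| 8 | 6.2 | 40% | 55% |

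**Missing data.** Missing echocardiographic values are not imputed, so 40 versus 20 is a ceiling. Protocol 15 aims to keep dropout within 20%. If that share lacked 24-hour data (an assumption), 32 versus 16 would be equivalent to 2 / (1/32 + 1/16) = 21.3 per group, with a half-width of 0.62 SD and a detectable difference of 0.88 SD.

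**The case against.** The strongest reply is that little depends on 4.1. It says openly that no formal calculation was made, so no power figure is wrong. The switch to separate cohorts is disclosed in several places, the 40 and 20 counts stand in the section just before, and SAP 7.7.1 requires a confidence interval for each treatment difference. The shortfall against 29 per group is only 4% in SE. All of this is true, and it limits the point to an outdated statement. It does not make that statement right: the sufficiency claim concerns istaroxime against placebo and names a placebo group that the primary analysis does not have.

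A second reply is that 40 versus 40 is an idealised benchmark. The protocol model was covariate-adjusted and the SAP model is not, so the net change in precision cannot be worked out from the documents. The extra 20 placebo patients also help only if there is no cohort effect: adding a cohort term to a treatment-only pooled model returns the SE to 0.274 SD, the 40 versus 20 value. This stands as a caution on the 67% and 22% figures. It leaves the head count and the 40 versus 20 precision unchanged.

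The reasons for the change are in a memo to file that is not among the documents. Precision may have been considered there; that cannot be checked.

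**Conclusion.** The point holds. SAP 4.1 states a size that the final primary analysis does not deliver: at most 40 versus 20, or 26.7 per group equivalent, against a stated forty and a cited 29. Compared with an unadjusted pooled 40 versus 40, information is one third lower and the SE 22% larger; compared with 29 versus 29, the SE is 4% larger. These figures assume a common SD and complete data, and the 40 versus 40 comparison also assumes no cohort effect. The power figures in E/Ea units rest on assumed SDs and are illustrative. The estimate is not biased and the test remains valid; what is wrong is the stated justification and the absence of any planned precision for the comparison actually made. It should be corrected.

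**What to change.** In SAP 4.1, delete the claim that forty per group will be sufficient and keep the statement that no formal calculation was made. Insert:

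> Echocardiographic comparisons use 40 istaroxime versus 20 placebo patients within each cohort, equivalent to 26.7 per group. With full evaluability this gives an expected 95% CI half-width of about 0.55 SD and 80% power (two-sided 0.05) to detect about 0.78 SD.

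In SAP 1.1, add one line saying that the protocol's forty-per-group rationale applied to the combined-cohort analysis. Protocol 14.2 can stay as it is. If power for the earlier study's effect is quoted, give it as a range over assumed SDs, including the low one.

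The cost is a few sentences in two sections. No patient, test, model or procedure changes. The stated justification becomes less favourable.

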# 4.2 RANDOMIZATION

The computer generated randomization list stratified by centre and atrial fibrillation (Yes/No) will be prepared via a computerised method. Starting from the lowest number provided, in each center and atrial fibrillation, at Day 1, patients will be sequentially assigned to the next randomization number, following the order in which they present themselves for the study.

1.0/30/10/2018 Page 10 of 28

#### 5.0 ANALYSIS SETS

#### INTENT-TO-TREAT POPULATION (ITT) 5.1

All randomized patients who will receive at least one administration of the study medication and with at least one available evaluation of efficacy after the baseline will be included in the ITT population.

The ITT population is the primary population for the efficacy analysis.

#### 5.2 PER-PROTOCOL POPULATION (PP)

All randomized patients from the ITT population without any major protocol deviation will be included in the PP population.

Exact definition of major protocol deviations will be discussed by the clinical team case by case during the blind review of the data.

#### SAFETY POPULATION 5.3

All randomized patients who will receive at least one administration of the study medication will be included in the safety population.

#### 5.4 OTHER ANALYSIS SET

All randomized patients will be included in the randomized population. The randomized population will be considered for descriptive purposes.

#### 5.5 TREATMENT MISALLOCATIONS

In case an error occurs in treatment allocation, the following rule will be followed: if a patient was randomized but received the incorrect treatment, he/she will be reported under his/her randomized treatment group for all analyses performed on the randomized and ITT populations, but he/she will be reported under the treatment actually received for all analyses performed on the safety. The patient will be excluded from the PP population.

#### PROTOCOL DEVIATIONS 5.6

All the protocol deviations will be discussed case by case before unblinding of the treatment code with the clinical team during the blind review of the data and described in the Data Review Report.

#### 6.0 **DEFINITIONS AND DATA CONVENTIONS**

This section contains definitions and conventions that will be used for the analysis.

1.0/30/10/2018

Page 11 of 28

# 6.1 DEMOGRAPHIC AND SCREENING/BASELINE CHARACTERISTICS VARIABLES

# General, demographic and baseline characteristics

### Age

If the date of birth is not missing, age will be calculated using the following rules:

• If month of date of screening is greater than month of date of birth or (month of date of screening is equal to month of date of birth and day of date of screening is greater than or equal to day of date of birth), then:

```
Age (years) = year (date of screening) - year (date of birth)
```

• Otherwise:

```
Age (years) = year (date of screening) – year (date of birth) - 1
```

In order to determinate the age of patient, the following rules will be applied for the partial date of birth:

- if only the day is missing, the 15th day of the month will be assumed;
- if the day and the month are missing, June 30th will be assumed.

If the date of birth is missing, the age recorded in the CRF will be used.

# Duration of smoking (years)

Duration of smoking will be calculated using the following formula:

- For ex-smoker:
  - Duration of smoking (years) = (stop date start date)/365.25
- For smoker:

Duration of smoking (years) =  $\frac{\text{date of screening} - \text{start date}}{365.25}$ 

In order to determinate the duration of smoking, the following rules will be applied for the partial dates of start/stop of smoking:

- for start date and stop date, the first day of the month will be assumed;
- if the month of start date or stop date is missing, January 1st will be assumed.

# Past disease and concomitant disease

#### Past disease

A disease is considered as past disease if it is not ongoing at screening visit ("ongoing" box is not ticked).

# Concomitant disease

A disease is considered as concomitant disease if it is ongoing at screening visit ("ongoing" box is ticked).

1.0/30/10/2018 Page 12 of 28

#### Previous and Concomitant medications

The following categories of medications will be identified:

- previous medication (start date < date of first randomized study medication intake and stop date ≤ date of first randomized study medication intake);
- medication maintained during the treatment period (start date < date of first randomized study medication intake and stop date > date of first randomized study medication intake or ongoing);
- concomitant medication (start date ≥ date of first randomized study medication intake).

In case of missing or incomplete dates not directly allowing allocation to any of the three categories of medications, a worst-case allocation will be done according to the available parts of the start/end dates. The medication will be allocated to the first category allowed by the available data, according to the following order:

- concomitant medication;
- medication maintained during the treatment period;
- previous medication.

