5.7 Concomitant Medication

All oral treatments, are permitted during the study with the exception of positive inotropic agents.

Dosage of oral HF medications must remain stable for at least 6 hours before study entry, during the entire treatment period (24-hour infusion), until 72 hours (on Day 4) after the start

of infusion on Day 1. Concomitant medications should be administered in the prerandomization phase and after at least 6 hours from the initiation of study drug infusion, if possible.

Intravenous diuretics administered during the screening period to stabilize the patient's condition will be permitted during the treatment period at stable doses, unless changes are required due to clinically relevant variations of the patient's condition.

Any introduction of new drugs or increase of the dosage of oral or i.v. medications for the treatment of heart failure, during treatment and till the 72 hours after the start of infusion (on day 4), will be considered as "rescue medication".

Patient supplementation of magnesium or potassium, prior to randomization, will not be considered as a change of the standardized therapy but just as a supplementation to maintain serum electrolytes within the normal ranges.

Administration of prior medications (i.e. drug treatments administered during the last month) and concomitant medications/therapies (i.e. medications ongoing at admission time and with a start date between admission to the research center and Day 4 or discharge) must be reported on the appropriate medication pages of the CRF, including dosage information, dates and time of administration and reasons for use. The international non-proprietary name and the trade name in brackets should be used for concomitant medications. The total daily dose or the stat dose, if appropriate, should also be reported. Rescue therapies will be recorded on the specific rescue medication page, recording the same information as for concomitant therapies, plus the time of administration of each single dose.

In case an inotrope should be necessary as rescue medication during the investigational product infusion period, the investigational product infusion should be terminated.

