- 6) NT pro-BNP at baseline and at the end of 24 hours infusion
- 7) Blood sample collection for metabolites and PK (at pre-dose, 0.5, 3, 6, 12, 24 hours after start of infusion and 0.25, 0.5, 1, 4, 12, 24, 48 hours after the end of infusion) in a subset of Italian patients and in a subset of Chinese patients pharmacokinetics and metabolism of istaroxime shall also be studied;
- 8) Vital signs (including arterial oxygen saturation and dyspnoea at pre-dose, 3, 6, 12 and 24 hours after the start of infusion);
- 9) 12-lead ECG profile (pre-dose, 3, 6, 12 hours and between 23 hours and 23 hours 55 minutes after infusion, totally 5 times, each time 3 measurements);
- 10)Stop 24-hour Holter ECG (Day -1 recording; Holter ECG monitor stops automatically 24 hours after the recording has been started;
- 11) Start 24-hour Holter ECG (Day 1 recording; to be started immediately before initiation of the study drug infusion);
- 12) Echocardiography at baseline and 6 and 24 hours after infusion start;
- 13) 24-hours urine collections for measurement of istaroxime and its metabolites and urinary

- creatinine for the calculation of the creatinine clearance
- 14) Blood collection for K+ and eGFR between 23 hours and 30 minutes and 23 hours and 55 minutes since infusion start
- 15) Concomitant medication monitoring (including chronic medication; dose, date and time must be recorded in the CRF);
- 16) Adverse events monitoring.

♦ Post-treatment period (Day 2 to Day 4)

Evaluations on Day 2 (end of the 24 hour infusion) include:

- 1) Vital signs (including arterial oxygen saturation and dyspnoea);
- 2) 12-lead ECG (triple ECGs) (between 23 hours and 23 hours 55 minutes since infusion start);
- 3) Stop 24-hour Holter ECG (Day 1 recording; to be stopped immediately after the end of study drug infusion;
- 4) Start 24-hour Holter ECG (Day 2 recording);
- 5) Stop istaroxime or placebo infusion (date and time of infusion end must be recorded in the CRF);
- 6) Serum potassium levels and 24-hour urine collection for measurement of istaroxime metabolites and urinary creatinine for calculation of the creatinine clearance;
- 7) Serum creatine clearance and calculation of eGFR;

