# Study medication intake

Date/time of first randomized study medication intake is the date/time of first study medication intake recorded at Day 1.

Date/time of last randomized study medication intake is the date/time of last study medication intake recorded in the Study Termination form.

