#### 6.4 SAFETY VARIABLES

#### Pre-treatment adverse events

An AE will be classified as pre-treatment AE if it starts before the date/time of first randomized study medication intake (AE onset date/time < date/time of first randomized study medication intake).

1.0/30/10/2018 Page 14 of 28

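### SAP 6.1 sorts medications by calendar date, so two groups of drugs at the infusion-start boundary fall into the wrong category in the descriptive medication tables

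*SAP*

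**What the plan says.** SAP 6.1, under Previous and Concomitant medications, defines three categories, all on dates:

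- For drugs already finished by the infusion date, the rule reads "previous medication (start date < date of first randomized study medication intake and stop date ≤ date of first randomized study medication intake".
- For drugs carried across that date, it reads "medication maintained during the treatment period (start date < date of first randomized study medication intake", with the added condition that the drug stops on a later day or is still running.
- For drugs begun on the infusion date or later, it reads "concomitant medication (start date ≥ date of first randomized study medication intake".

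A worst-case order (concomitant, then maintained, then previous) applies only where dates are missing or incomplete.

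The next item of the same section, Study medication intake, defines the boundary to the time of day: "Date/time of first randomized study medication intake is the date/time of first study medication intake recorded at Day 1". SAP 6.4 uses that definition for adverse events, where an event is pre-treatment if "AE onset date/time < date/time of first randomized study medication intake". SAP 6.2 also computes exposure from infusion start and end date/time.

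On data collection, Protocol 5.7 asks for medication records "including dosage information, dates and time of administration and reasons for use", and the Day 1 list in Protocol 7 says of concomitant medication that "dose, date and time must be recorded in the CRF".

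SAP 7.6 uses the three categories for frequency tables by treatment group in the ITT population.

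**The concern.** In a long trial, one ambiguous calendar date hardly matters. Here screening takes at most 24 hours, the infusion lasts 24 hours and the primary endpoint is read at 24 hours. Protocol 5.7 also concentrates drug use around the boundary: intravenous diuretics are given during screening to stabilise the patient, and concomitant drugs are to be given before randomisation where possible.

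A date-only rule errs in both directions. Stabilising therapy given on the morning of the infusion appears as therapy added on treatment, and a drug that ran during part of the infusion appears as already finished. The second error also runs against the SAP's own caution. With incomplete dates the SAP assigns *previous* last, yet with complete dates a drug that overlapped the infusion goes there.

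What is at stake is how readable the tables are when someone asks whether the arms received similar co-treatment around the infusion. Therapy given before dosing cannot be affected by study treatment, so mixing it into *concomitant* blurs any difference between arms in therapy added afterwards.

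**Working it through.** The plan gives no figure to reproduce. The check applies the rule as written, and the same rule on date/time, to constructed records.

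**Inputs.** The category definitions come from SAP 6.1, the screening window (hours -24 to -1) from Protocol 7, and the 24-hour infusion from the Protocol synopsis. The documents give no clock time for infusion start; Day 1 14:00 is an assumption, varied below.

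**Step 1: eight test records, infusion start Day 1 14:00.**

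| Start | Stop | Date rule (SAP 6.1) | Date/time rule |
|---|---|---|---|
| months earlier | ongoing | maintained | maintained |
| Day -1 20:00 | ongoing | maintained | maintained |
| Day 1 08:00 | Day 1 09:00 | **concomitant** | **previous** |
| Day 1 08:00 | ongoing | **concomitant** | **maintained** |
| Day -1 20:00 | Day 1 22:00 | **previous** | **maintained** |
| Day -1 20:00 | Day 1 10:00 | previous | previous |
| Day -1 20:00 | Day 2 02:00 | maintained | maintained |
| Day 1 16:00 | ongoing | concomitant | concomitant |

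Three of the eight change. In the fifth row the drug ran for 22 - 14 = 8 hours of the infusion and is still labelled previous. The records were chosen to probe the boundary, so 3 of 8 is not an error rate.

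**Step 2: how much of the screening window is exposed to the first error.** The window from -24 h to -1 h is 23 hours long. For infusion start at clock hour h, the part on the infusion date runs from midnight to h - 1, so the share is (h - 1)/23:

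- 08:00: 7/23 = 30%
- 14:00: 13/23 = 57%
- 20:00: 19/23 = 83%

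**Step 3: how long a drug labelled previous can overlap the infusion.** The infusion hours on the start date number 24 - h, which is the upper limit of the overlap:

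- 08:00: 16 h
- 14:00: 10 h
- 20:00: 4 h

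A later start widens the first error and narrows the second. Both are possible throughout the assumed 08:00 to 20:00 range.

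**Step 4: does another rule repair it?** The worst-case order does not, because it needs a missing or incomplete date. A complete same-day date never reaches it.

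**The case against.** The strongest reply is that this is a boundary defect in descriptive tables. Much of it stands.

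- **No analysis depends on the categories.** The models in SAP 7.2 and 7.7 do not use them, and no analysis set in SAP 5 is defined by them. The rule is the same for all arms, so it blurs the comparison and does not obviously favour one arm. This stands.
- **Protocol rules shrink both groups.** Protocol 5.7 requires oral heart-failure doses to be stable from 6 hours before entry to 72 hours, and exclusion criterion 2 restricts intravenous vasodilators, inotropes and vasopressors. The Day -1 Holter also suggests that screening often starts on the previous date. This limits the number of records. It does not remove the defect, since the window permits same-day screening and intravenous diuretics are allowed.
- **Other views of added therapy exist.** SAP 7.7.2 summarises worsening heart failure, defined by increased or restarted intravenous therapy, at Days 2, 3 and 4, and SAP 7.4 lists all CRF data. A reader might infer that the medication tables are the only view of co-treatment, so that an E/Ea result could not be checked against it. The documents do not support that. The worsening summary does not name drugs, however, and the SAP plans no table from the rescue-medication page.
- **Stop times may be missing.** Protocol 5.7 and 7 ask for a time of administration, but neither names a stop time, which the second error needs. This stands and bears on the fix.
- **The protocol counts concomitant therapy from admission.** Protocol 5.7 does use such a reporting window. The SAP's categories are set relative to first study drug intake, though, and under the protocol's window a drug started after admission on Day -1 would also be concomitant, which the SAP rule does not allow. The date rule therefore matches neither definition.

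**Conclusion.** The rule in SAP 6.1 gives wrong categories for two groups: drugs started on the infusion date before the infusion, and drugs started on an earlier date and stopped on the infusion date after infusion start. This follows from the wording and needs no assumption.

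A reader might infer that pre-infusion background therapy in general is counted as on-treatment. It is not: chronic drugs, and drugs begun on an earlier date that continue past Day 1, are correctly *maintained*.

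The consequence is limited to the by-arm medication tables of SAP 7.6. No estimate, confidence interval or p-value changes. The shares of 30%, 57% and 83% are clock arithmetic at assumed start hours. They should not be read as shares of drugs, records or patients, which the documents do not allow anyone to derive. The defect is worth correcting because it lies at the hours around the primary assessment and the SAP already contains the definition needed.

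**What to change.** In SAP 6.1, replace date with date/time in all three medication categories, comparing medication start and stop date/time with the date/time of first study medication intake as SAP 6.4 does for adverse events. State that the existing worst-case order also applies when a start or stop time is missing. A drug started on an earlier date and stopped on the infusion date at an unknown time then becomes *maintained*; one started on the infusion date at an unknown time stays *concomitant*.

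Optionally, split *concomitant* in the SAP 7.6 tables into therapy started during the infusion and therapy started after it. The tables count each patient once per preferred name and carry no dose, so even corrected categories will not show whether diuretic exposure was equal between arms.

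The cost is three lines of SAP text and minor programming. Check first that the CRF holds stop times; records without one fall to the worst-case rule.
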